8.1. Statistical considerations

All statistical tests will be two-sided and at the 5% level of significance.

8.2. Descriptive analysis

Descriptive statistics will be provided by one treatment group according to criteria nature:

- Quantitative: number of observed values (nobs), mean, standard deviation (SD), standard error (SE), median, 1st and 3rd quartiles (Q1:Q3), minimum and maximum.
- Qualitative: number of observed values (nobs), number (n) and percentage (%) of patients per class The number of subjects by treatment group in the subject set (N) will be also given.

Descriptive statistics will be performed on per protocol population and will be provided for all demographic and baseline characteristics:

- ✓ Age
- ✓ Gender
- ✓ All attributes of Clinical Assessment Score
- ✓ Score of LA Sting Test
- ✓ Value of Instrumental Measurement Value
- ✓ Value of Imaging Analysis (OCT)

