Investigator: Title: Dermatologist

[contact] [contact]

Test Site: China-Norm U@Test laboratory

Address: [name],

Shanghai, China

Study Objective: To evaluate the effect of a facial essence on skin barrier and skin condition after 2-week of use; And study on the repair efficacy of skin barrier and condition after receiving Fractional Ultrapulse CO₂-laser. The whole study will be divided into two dimensions to evaluate the product: the comparison of the effect before and after and the comparison with the control group.

Experimental Design:

Mono-centric, single-blind, parallel random and home use design.

Test Areas:

Whole face

Subjects:

70 female adult subjects will be enrolled and divided into 2 groups in the study, recruited according to inclusion and non-inclusion criteria listed below, and at least 60 subjects should complete the whole study (at least 30 subjects per group).

Group 1: Facial Serum Group

- Group 2: Non-treatment Group

Age: 20-50 years old

Measurements:

Clinical Assessment(N=60):

Skin qualities of skin dryness, erythema, papules, desquamation, chromatosis, edema, escharosis, elasticity, evenness, brightness, radiance, smoothness, pores on cheek, crow's feet wrinkle, epithelial confluence and overall healthy appearance will be evaluated by dermatologist at T0 (baseline), T14d (after pre-treatment), T15d (Timm post-procedure), T16d (1-day after self-recovery), T18d (3-day after self-recovery), T22d (7-day after self-recovery), T25d (10-day after self-recovery and product treatment start), T32d (7-day after product treatment), T39d (14-day after product treatment) for all groups.

Lactic Acid Stinging Test (N=60)

Sensitive level by Lactic acid test at T0 (baseline), T14d (after pre-treatment), T25d (10-day after self-recovery and product treatment start), T39d (14-day after product treatment) for all groups.

Instrument Assessment(N=60):

- **Corneometer:** skin hydration on both cheeks will be measured at T0 (baseline), T14d (after pre-treatment), T15d (Timm post-procedure), T16d (1-

day after self-recovery), T18d (3-day after self-recovery), T22d (7-day after self-recovery), T25d (10-day after self-recovery and product treatment start), T32d (7-day after product treatment), T39d (14-day after product treatment) for all groups.

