- 13. Must be willing to comply with all study protocol requirements (pay attention to: only use the skin care products provided during the study, not take topical or oral treatment like retinol, hormone, anti-oxidant health-care products which may affect the anti-aging efficacy of test serum).

Exclusion Criteria:

Prospective subjects meeting any of the criteria listed below will be excluded from participation:

- 1. Pregnant or breast-feeding woman or woman planning pregnancy during the study.
- 2. Subject deprived of rights by a court or administrative order.
- 3. Major subject to a guardianship order.
- 4. Subject residing in a health or social care establishment.
- 5. Patient in an emergency setting.
- 6. Subject with a skin disease in the test areas as well as skin allergy (particularly e.g., acne, rosacea, eczema).
- 7. Volunteer presenting a stable or progressive serious disease (per investigator's assessment).
- 8. Immuno-compromised subject.
- 9. Subject has hyperpigmentation skin symptoms.
- 10. Subject with history of allergy to cosmetic or personal care products or ingredients.
- 11. Subject presenting excessive exposure to sunlight or UV radiation (investigator's assessment).
- 12. Subjects regularly practicing aquatic or nautical sports.
- 13. Subjects regularly attending a sauna.
- 14. Subject with physical highly sensitive constitution;

¹Declaration of Helsinki, 64th World Medical Assembly, Fortaleza, Brazil, October 2013

- 15. Subject with cardiovascular or circulatory history.
- 16. Subject with a history of skin cancer or malignant melanoma.
- 17. Subject with history of medical beauty treatment and taking part in anti-aging studies in the last 3 months before study.
- 18. Intake of antihistamines, antibiotics, corticosteroids, non-steroidal anti-inflammatories or immune-suppressants in the last 6 months before study.

4. Study Design

70 female adult subjects will be enrolled and divided into 2 groups in the study, recruited according to inclusion and non-inclusion criteria listed below, and at least 60 subjects should complete the whole study (at least 30 subjects per group).

• Clinical Assessment(N=60):

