• Photo Capture and Imaging Analysis(N=60):

- VISIA 7: standard facial photos shooting will be done at T0 (baseline), T14d (after pre-treatment), T15d (Timm

post-procedure), T16d (1-day after self-recovery), T18d (3-day after self-recovery), T22d (7-day after self-recovery), T25d (10-day after self-recovery and product treatment start), T32d (7-day after product treatment), T39d (14-day after product treatment) for all groups.

- **OCT:** standard facial scan will be done at T0 (baseline), T14d (after pre-treatment), T15d (Timm post-procedure), T16d (1-day after self-recovery), T18d (3-day after self-recovery), T22d (7-day after self-recovery), T25d (10-day after self-recovery and product treatment start), T32d (7-day after product treatment), T39d (14-day after product treatment) for all groups.

• Self-Assessment(N=60):

- **Self-Assessment Questionnaire on product efficacy** will be answered by subjects at T14d (after pre-treatment), T25d (10-day after self-recovery), T32d (7-day after product treatment), T39d (14-day after product treatment) for Group 1 (N=30);
- **Self-Assessment Questionnaire on cosmeticity** will be answered by subjects at T14d (after pre-treatment), T39d (after product treatment) for Group 1 (N=30).
- **Self-assessment questionnaire on post-procedure tolerance** will be answered by subjects at T15d (Timm post-procedure), T16d (1-day after self-recovery), T18d (3-day after self-recovery), T22d (7-day after self-recovery), T25d (10-day after self-recovery) for all groups (N=60).

1) Study Schedule:

	Wash-out	Pre-tre	eatment	Chemi	cal Procedure		10-day Self-recover	у		Post-treatment	
Activities	V1	V2	V3		V4	V5	V6	V7	V8	V9	V10
	T-7d	T0 (baseline)	T14d (after pre- treatment)	T15d	T15d-Timm (post-procedure)	T16d (1-day after self- recovery)	T18d (3-day after self-recovery)	T22d (7-day after self- recovery)	T25d (10-day after self- recovery & post- treatment start)	T32d (7-day after post- treatment)	T39d (7-day after post- treatment)
Written informed consent	X										
Inclusion / non-inclusion Criteria (Primary eligibility)	X										
Medical history	X										
Pregnancy test	X										
Clinical grading by dermatologist	X only screening	X	X		X	X	X	X	X	X	Х
CO2 laser				X							
VISIA 7		X	X		X	X	X	X	X	X	X
OCT		X	X		X	X	X	X	X	X	X
Lactic acid Sting Test		X	X						X		X
Corneometer		X	X		X	X	X	X	X	X	X
Vapometer		X	X		X	X	X	X	X	X	X
Cutometer		X	X		X	X	X	X	Х	X	X
pH meter		X	X		X	X	X	X	X	X	X
Self-assessment QNs			X		X	X	X	X	X	X	X

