7.2. Conducting the Study

Pre-screening visit at T-7d

- a. Within 24 hours before screening visit, subjects will be asked not to use any cosmetic product on test areas.
- b. On the arrival, the subject will be informed about the nature of the study and the treatment procedure and a signed and dated informed consent form will be obtained. At the same time, one Photo release form will be also signed from each subject.
- c. A subject screening number will be automatically allocated (SC0X) by CRF.
- d. Demographic data collection.
- e. Medical examination, subject's interview on his medical history and concomitant medications.
- f. Subjects wash face with usual cleanser, then pat dry with clean tissue paper at center.
- g. Acclimatization to the room condition for 30 minutes (the conditions with a well-controlled room temperature (21 ± 1 °C) and humidity ($45\%\pm5\%$).
- h. Clinical assessment by will be done by dermatologist for screening.
- i. Verification of subject eligibility: inclusion/non-inclusion criteria and on-site clinical grading by Dermatologist.
- j. The weighted wash-out products and daily log will be delivered to each subject.
- k. Adverse Events/Local Intolerance will be checked and recorded.

Evaluation visit on T0: Baseline

- a. Subjects wash face with usual cleanser, then pat dry with clean tissue paper at center.
- b. Acclimatization to the room condition for 30 minutes (the conditions with a well-controlled room temperature (21 ± 1 °C) and humidity ($45\%\pm5\%$).
- c. Verification of inclusion/non-inclusion criteria for final eligibility.
- d. Clinical Assessment will be done by dermatologist for T0.
- e. VISIA 7 will be done by trained technician for T0.
- f. OCT scan will be done by trained technician for T0.
- g. Corneometer will be done by trained technician for T0.
- h. Vapometer will be done by trained technician for T0.
- i. Cutometer will be done by trained technician for T0.
- j. pH meter will be done by trained technician for T0.

- k. LA sting test will be done by trained technician for T0.
- The wash-out (standard) products will be weighted and returned to subjects; as the same time, the weighted
 investigational products and daily log will be delivered to each subject according to the randomization
 table.
- m. Adverse Events/Local Intolerance will be checked and recorded.

T0 to T14d

a. Subjects should apply the provided wash-out products twice a day at home, in the morning and in the evening.

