8.3. Efficacy Verification

8.3.1 Comparison between Time-points

A Shapiro-Wilk test will be used to test for normality of the baseline data (T0) and the change from baseline data (Tn-T0) at post-baseline time points at significance level alpha=0.01. When data passes normality (all normality of the distributions is confirmed for the same parameter), a parametric test will be used to test the null hypothesis that the mean change from baseline is zero. When data fails normality (if one or more normality of the distributions for the same parameter is rejected), a non-parametric test will be used.

Pre-treatment efficacy:

- a) T14d (after pre-treatment), T15d (Timm post-procedure) versus T0 (baseline)
- b) T16d (1-day after self-recovery), T18d (3-day after self-recovery), T22d (7-day after self-recovery), T25d (10-day after self-recovery) versus T15d (Timm post-procedure)

Post-treatment efficacy:

a) T32d (7-day after product treatment), T39d (14-day after product treatment) versus T25d (product treatment start)

The following will be calculated and reported for each evaluation parameter at applicable post-statistical baseline time point(s):

For self-assessment questionnaires, only the data of completing subjects will be analyzed. Questionnaire response options will be in the form of a 5-point semi-structured scale, ranging from one (1) to (5), where the score of one (1) will be the most negative/unfavorable rating and the score of five (5) will be the most positive/favorable rating the product can receive (the scale will also include a mid-point label "neither agree nor disagree"). Responses obtained for each question will be tested for normality using a Shapiro-Wilk test at significance level alpha=0.01, and if the data passes normality testing, mean scores will be used. Responses that are not normally distributed will be assessed using the median response. The percentage of ratings from

4 to 5 ("top XX box %") will be reported.

In the report appendices, raw data and open-ended questionnaire responses will be listed by subject. Data frequency and percentage will be presented for questionnaires and tolerability evaluations. Tolerability tables will also be sent to the Sponsor at the indicated interim data time points; SAQ data will be sent at study completion, for all completing subjects. Medians, means and percentage values will be reported to decimal place (0.0) for all questionnaire data.

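### The only analysis set the protocol names is an undefined per-protocol set, used even for baseline, and questionnaires drop the answers of anyone who later leaves

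*Protocol*

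**What the plan says.** The design is "Mono-centric, single-blind, parallel random and home use design". On size, the synopsis and section 4 say that "70 female adult subjects will be enrolled and divided into 2 groups in the study" and that "at least 60 subjects should complete the whole study (at least 30 subjects per group". Allocation takes effect at T0, where section 7.2 has the "investigational products and daily log will be delivered to each subject according to the randomization" table.

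Two rules restrict who is analysed:

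- **Section 8.2:** "Descriptive statistics will be performed on per protocol population", and the same sentence extends this to every demographic and baseline characteristic. The list that follows covers age, gender, all clinical scores, the lactic acid score, the instrumental values and the OCT values. No definition of the per-protocol population appears anywhere in the protocol.
- **Section 8.3.1:** "For self-assessment questionnaires, only the data of completing subjects will be analyzed". The same section later limits the questionnaire data sent to the sponsor to completing subjects.

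The efficacy and cosmeticity questionnaires go to one group only; the schedule for the efficacy questionnaire ends with "T39d (14-day after product treatment) for Group 1 (N=30". The post-procedure tolerance questionnaire goes to both groups at T15d, T16d, T18d, T22d and T25d (section 5.6).

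Section 8.3.2, which compares Group 1 with Group 2, names no population. Section 9.2 asks only that the reason for a withdrawal be documented and reported. The assessment headings in sections 4 and 5 carry N=60, the completer target, and not 70.

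**The concern.** Per-protocol and completer sets are formed after allocation, by events that treatment can influence. Two consequences follow directly from what the protocol states.

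First, a baseline table is there to show what randomisation produced. If subjects are removed for deviations or withdrawal before the table is made, it describes the survivors of that selection. An imbalance may be created or hidden by the exclusions, and the reader cannot tell which. As the set is undefined, the exclusions could also be decided after the data are seen.

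Second, the completers rule deletes valid observations. A subject who reports poor tolerance the day after the laser and then withdraws loses that report from the analysis. Tolerance is the outcome for which this matters most, because a bad answer and leaving the study plausibly go together. For the Group 1 questionnaires, dissatisfied subjects who leave would drop out of the denominator, and the top-box percentage would rise.

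A third consequence is conditional. If the group comparison in 8.3.2 also used only completers or the per-protocol set, the estimated difference could carry selection bias.

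**Working it through.** **The plan's own figures.** The protocol gives no effect size, SD, power or dropout rate, so there is no power-based sample size to reproduce. The figures available are 70 enrolled and at least 60 completing:

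- Planned allowance: 70 − 60 = 10; 10/70 = 14.3%.
- With a 1:1 split (assumption; the split is not stated): 35 − 30 = 5 per group; 5/35 = 14.3%.

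This is an allowance and not an upper limit. Sixty is a minimum target that may be missed, and an undefined per-protocol set can also remove completers with deviations. Nor need all 10 be lost after randomisation: final eligibility and allocation come at T0, after consent and a 7-day wash-out, so some may leave before they are allocated.

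**What a leaver has already contributed.** The post-T0 assessments are T14d, T15d, T16d, T18d, T22d, T25d, T32d and T39d, eight in all. Someone who leaves before T39d has at most seven. Someone who leaves between T25d and T39d can have answered all five tolerance questionnaires, and the completers rule removes all five.

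**Group 1 top-box percentage.** Assume 35 allocated, 30 completing, and 24 of the 30 rating 4 or 5.

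- Reported: 24/30 = 80.0%.
- If none of the 5 missing subjects would rate 4 or 5: 24/35 = 68.6%.
- If all 5 would: (24 + 5)/35 = 29/35 = 82.9%.

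The possible overstatement (11.4 points) is larger than the possible understatement (2.9 points).

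**Group difference, if 8.3.2 were run on completers.** Let the 5 lost in one group differ from that group's completers by s SD, and let loss in the other group be unrelated to outcome. The mean of all 35 is the completer mean plus (5/35) × s, so the completer difference is biased by (5/35) × s in absolute size. The approximate two-sided 5% error uses a standard error of √(2/30) = 0.258 SD.

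| s (assumed) | Bias = (5/35) × s | Bias / 0.258 | Approximate type I error |
|---|---|---|---|
| 0.5 SD | 0.07 SD | 0.28 | 5.9% |
| 1.0 SD | 0.14 SD | 0.55 | 8.6% |
| 1.5 SD | 0.21 SD | 0.83 | 13.2% |

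For scale, the difference detectable with 80% power at 30 per group is (1.960 + 0.842) × √(2/30) = 0.72 SD. The bias would be about 10% to 30% of that (0.071/0.723 to 0.214/0.723). With 35 per group and complete data, the detectable difference would be 2.802 × √(2/35) = 0.67 SD.

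**The case against.** **The two rules do not govern the group comparison.** A reader might infer that efficacy is to be compared per protocol and that 10 randomised subjects will leave that comparison. The documents do not say so. Section 8.2 covers descriptive statistics of demographic and baseline characteristics, the completers rule covers questionnaires, and 8.3.2 is silent. A separate SAP may name the population, and its absence here is not an error. The N=60 headings are weak evidence, because they also cover T0, when everyone attending is measured. This objection stands, and it limits the firm part of the point to baseline tables and questionnaires.

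**Most questionnaires have no control group.** The efficacy and cosmeticity questionnaires are answered by Group 1 only, so there is no randomised contrast to bias. This is correct; the harm there is a distorted percentage. It does not cover the tolerance questionnaire, which both groups answer.

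**The direction of bias is not established.** It is tempting to say that dropping leavers favours the product, since only Group 1 can leave because of the serum. But both groups receive the laser and the same regimen from T15d to T24d (section 6.2), and loss for slow healing could be as common or more common in Group 2. The direction is therefore unknown.

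**Exits are recorded.** Withdrawal reasons, adverse events and local intolerances are reported throughout. This helps, but it does not restore discarded answers or a baseline table of the groups as randomised.

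**An SAP could repair everything.** For 8.3.2, yes. For the other two rules it would have to contradict the protocol. The allowance in 8.3.1 for a more appropriate analysis, recorded in a note to file or the study report, is no safeguard because it fixes nothing beforehand.

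**Conclusion.** The point holds for what the protocol fixes: an undefined per-protocol set as the only named population, applied to baseline description, and a completers-only rule that discards answers already collected, including those on a questionnaire given to both groups. Neither conclusion needs an assumption.

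The sizes do rest on assumptions. With 35 allocated to Group 1 and 5 lost, an 80% top-box result is compatible with 68.6% to 82.9%. A bias of 0.07 to 0.21 SD in the group difference applies only if 8.3.2 is run on completers, the split is 35/35, the 5 lost in one group differ by 0.5 to 1.5 SD, and loss in the other group is uninformative.

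A reader might go further and conclude that the protection of randomisation is lost. That is too strong. For 8.3.2 no restriction is stated. Where exclusions do occur, the protection is weakened by an amount that depends on how far loss differs between groups and is related to outcome. The matter deserves correction because the remedy is cheap, not because bias has been shown.

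**What to change.** 1. In 8.2, tabulate demographic and baseline characteristics for all randomised subjects, by assigned group.
2. In 8.3.1, replace the completers rule: analyse each questionnaire for everyone who answered at that visit, and print the number randomised to the group beside the number answering.
3. For 8.3.2, name all randomised subjects, in their assigned group and with all available data, as the main set.
4. Define the per-protocol population before the data are examined, and keep it as a sensitivity analysis.

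None of this alters visits, measurements or sample size, and none of it requires a different statistical model; the choice of test is a separate question. The cost is revised wording and one extra set of tables. Estimates may turn out slightly less favourable to the product.

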8.3. Efficacy Verification

8.3.1 Comparison between Time-points

A Shapiro-Wilk test will be used to test for normality of the baseline data (T0) and the change from baseline data (Tn-T0) at post-baseline time points at significance level alpha=0.01. When data passes normality (all normality of the distributions is confirmed for the same parameter), a parametric test will be used to test the null hypothesis that the mean change from baseline is zero. When data fails normality (if one or more normality of the distributions for the same parameter is rejected), a non-parametric test will be used.

Pre-treatment efficacy:

- a) T14d (after pre-treatment), T15d (Timm post-procedure) versus T0 (baseline)
- b) T16d (1-day after self-recovery), T18d (3-day after self-recovery), T22d (7-day after self-recovery), T25d (10-day after self-recovery) versus T15d (Timm post-procedure)

Post-treatment efficacy:

a) T32d (7-day after product treatment), T39d (14-day after product treatment) versus T25d (product treatment start)

The following will be calculated and reported for each evaluation parameter at applicable post-statistical baseline time point(s):

For self-assessment questionnaires, only the data of completing subjects will be analyzed. Questionnaire response options will be in the form of a 5-point semi-structured scale, ranging from one (1) to (5), where the score of one (1) will be the most negative/unfavorable rating and the score of five (5) will be the most positive/favorable rating the product can receive (the scale will also include a mid-point label "neither agree nor disagree"). Responses obtained for each question will be tested for normality using a Shapiro-Wilk test at significance level alpha=0.01, and if the data passes normality testing, mean scores will be used. Responses that are not normally distributed will be assessed using the median response. The percentage of ratings from

4 to 5 ("top XX box %") will be reported.

In the report appendices, raw data and open-ended questionnaire responses will be listed by subject. Data frequency and percentage will be presented for questionnaires and tolerability evaluations. Tolerability tables will also be sent to the Sponsor at the indicated interim data time points; SAQ data will be sent at study completion, for all completing subjects. Medians, means and percentage values will be reported to decimal place (0.0) for all questionnaire data.

A more appropriate analysis may be performed, which will be recorded in a Note to File and/or in the study report.

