5.2. Lactic Acid Test (N=60)

The lactic acid test is widely accepted as a marker of skin sensitivity and employed for the selection of subjects experiencing invisible sensory irritation. A self-assessment questionnaire (Annex 11.4) of the intensity of symptoms (stinging, itchiness, burning and other) will be answered by subject at 30 seconds, 2.5 minutes, 5 minutes after lactic application. The variation of score between 10% concentration of lactic and distilled water will be calculated and defined to the sensitive level. This process will be done at T0 (baseline), T14d (after pre-treatment), T25d (10-day after self-recovery and product treatment start), T39d (14-day after product treatment)

Score 0: Not at all

Score 1: Slight

- Score 2: Moderate

- Score 3: Severe

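### Section 8.3.1 labels within-group change from T15d and T25d as efficacy, although healing after the laser would produce it in either group; efficacy should rest on the T0-adjusted group comparison

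*Protocol*

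**What the plan says.** Section 8.3 of the protocol covers efficacy. Its first part, 8.3.1, sets the hypothesis: "a parametric test will be used to test the null hypothesis that the mean change from baseline is zero". There is no control term. It then lists three sets of contrasts.

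- Pre-treatment efficacy, item (a): "T14d (after pre-treatment), T15d (Timm post-procedure) versus T0 (baseline".
- Pre-treatment efficacy, item (b): T16d, T18d, T22d and finally "T25d (10-day after self-recovery) versus T15d (Timm post-procedure".
- Post-treatment efficacy: T32d and "T39d (14-day after product treatment) versus T25d (product treatment start".

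The second part, 8.3.2, compares Group 1 with Group 2 on clinical, instrumental, imaging, lactic acid and tolerance attributes. It does not name the visit, or say whether a level or a change is compared, or from which reference.

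Three other places matter.

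- Section 7.2 has the T15d measurements follow the CO2 laser at the same visit.
- Section 6.2 has Group 1 use the serum from T0 to T14d and again from T25d. From T15d to T24d both groups follow one recovery regimen that does not include the serum.
- Section 5.2 fixes the lactic acid schedule: "This process will be done at T0 (baseline), T14d (after pre-treatment), T25d" and T39d. T15d is not among the visits.

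**The concern.** The second study objective concerns repair of the skin after the laser. Item (b) addresses it by asking whether skin improves from its state just after injury. Untreated skin does that as well, so a significant result in Group 1 says nothing about the serum. T15d versus T0 has a related fault: the laser falls between the two visits, yet the contrast is called efficacy. The post-treatment line counts any healing that continues after T25d, together with the return to standard products in both groups.

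T15d and T25d also come after 14 days of serum in Group 1. If the serum softens the laser insult, that benefit sits in the reference value and is subtracted from every change measured from it.

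At stake is whether a before/after p-value produced by healing is read as evidence for the product, and whether a real protective effect is missed.

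**Working it through.** **Inputs from the protocol.** Section 8.1: "All statistical tests will be two-sided and at the 5% level of significance". Study Design: "70 female adult subjects will be enrolled and divided into 2 groups in the study", and "at least 60 subjects should complete the whole study (at least 30 subjects per group". Going from 70 to 60 allows for 1 − 60/70 = 14.3% loss. No effect size, SD or power is attached, so there is no sample-size figure to reproduce, and none is disputed here. I use n = 30 per group.

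**Step 1: what lies between the visits of each contrast (sections 6.2 and 7.2).**

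| Contrast | Group 1 | Group 2 |
|---|---|---|
| T14d v T0 | serum and standard products | standard products |
| T15d v T0 | the same, plus the laser | the same, plus the laser |
| T16d to T25d v T15d | recovery care, no serum | identical recovery care |
| T32d, T39d v T25d | serum, standard products, any remaining healing | standard products, any remaining healing |

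Only T14d v T0 is free of the laser. In the third row nothing given during the interval differs between the groups.

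**Step 2: the one-sample test when the product does nothing.** Let h be the mean healing in units of the SD of the change. The noncentrality is δ = h√30, and the test rejects when |t| exceeds 2.045 (29 df). The values of h are assumed.

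| h | δ | Probability of a significant change |
|---|---|---|
| 0 | 0 | 5% |
| 0.25 | 1.37 | 26% |
| 0.5 | 2.74 | 75% |
| 0.75 | 4.11 | 98% |
| 1 | 5.48 | over 99.9% |

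**Step 3: what happens to protection.** Take higher as worse. Let the laser add L at T15d and let Group 2 be back to zero at T25d. Let the serum lower the mean by p15 at T15d and by p25 at T25d.

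- Change from T15d to T25d, Group 1: (−p25) − (L − p15) = −L + p15 − p25.
- The same in Group 2: −L.
- Difference, Group 1 minus Group 2: p15 − p25.

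If the protection persists (p25 = p15) the difference is 0 and the benefit is invisible. If the gap closes as both groups heal (p25 = 0) the difference is +p15, which counts against the serum. By contrast, T15d minus T0 compared between groups gives −p15, which keeps the benefit.

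**Step 4: size, by simulation.** All inputs are assumed: SD 1 at each visit, within-subject correlation 0.5 (so the SD of a change is √(2 × 0.5) = 1), L = 1.5, 30 per group, 4,000 runs.

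| p15, p25 | Mean difference in change from T15d | That change significantly against serum | That change significantly for serum | T15d − T0 between groups, for serum | T25d level, for serum |
|---|---|---|---|---|---|
| 0, 0 | 0.00 | 2.6% | 2.6% | 2.1% | 2.4% |
| 0.5, 0 | +0.50 | 48% | 0% | 49% | 3.0% |
| 0.75, 0 | +0.76 | 82% | 0% | 82% | 2.4% |
| 0.5, 0.5 | 0.00 | 2.7% | 2.4% | 48% | 48% |
| 0.75, 0.75 | 0.00 | 2.4% | 2.6% | 81% | 82% |

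In the first row the within-group change from T15d was significant in 100% of runs in both groups, with no product effect at all. The group comparisons there stay near 2.5% in the serum's favour, as they should at a two-sided 5% level.

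**Step 5: lactic acid.** T25d appears as an outcome visit only in item (b), against T15d. With no T15d reading, 8.3.1 leaves the lactic acid result at T25d without a usable reference. T14d v T0 and T39d v T25d remain computable.

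**The case against.** The best reply is that 8.3.1 does not stand alone. The objective names two dimensions, before/after and comparison with control, and 8.3.2 supplies the second. Healing common to both groups cancels there. That stands, and it limits the point: the protocol does plan a valid kind of comparison. That 8.3.2 leaves visit and quantity open may be settled in an analysis plan not at hand, so this silence is not the fault. The fault is what 8.3.1 does fix, namely contrasts and labels that call healing efficacy.

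Second, item (a) uses T0, which precedes both serum and laser, and T14d v T0 is clean of the laser. That also stands. The objection to item (a) is confined to T15d v T0, where the injury lies in the outcome visit.

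Third, T25d is a reasonable starting point for the added effect of the second course. It is, if the change is compared between groups. Within one group it still counts continued healing.

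Fourth, 8.3.1 limits reporting to applicable time points, so the missing lactic acid reading at T15d may simply mean that the contrast is not run. That is fair. It makes this a gap at T25d, not a separate error.

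Fifth, T14d might seem the natural replacement reference. It also follows 14 days of serum in Group 1, so using it in the group comparison would subtract any benefit already gained by then.

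**Conclusion.** The point holds for item (b), for the post-treatment line and for T15d v T0. As tested in 8.3.1, these changes cannot show a serum effect. Once healing reaches about 0.75 SD of the change, the test from T15d is significant in 98% or more of trials with an inert product, in the untreated group as well. How much the T25d contrasts are inflated depends on how much healing remains by then, which the protocol does not say.

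The loss of earlier protection from changes measured from T15d or T25d follows from the arithmetic. Its consequence for the group comparison is conditional.

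A reader might go further and infer that the trial would be declared successful on healing alone. The documents do not support this: there is no stated success rule, and a group comparison is planned. A reader might also infer that a real benefit will come out with the wrong sign. That needs 8.3.2 to compare groups on change from T15d, which it neither states nor excludes, and it needs the gap between groups to close with healing. If the protection persists, the benefit is hidden, not reversed. The 48% and 82% illustrate the mechanism under assumed SD, correlation and effect sizes and are not forecasts for this trial.

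**What to change.** Change the wording of 8.3.1 and 8.3.2; every visit needed is already scheduled.

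- State in 8.3.2 that efficacy conclusions rest on Group 1 versus Group 2 at each visit, adjusted for T0, for example by ANCOVA on the visit value with T0 as covariate. Include lactic acid at T14d, T25d and T39d, which also removes its dependence on a T15d reading.
- In 8.3.1, relabel the changes from T15d and from T25d, and T15d versus T0, as a description of injury and healing in each group.
- Optionally add T15d to T25d versus T14d as a descriptive measure of return to the pre-laser state. Note that T14d is itself post-randomisation and does not replace T0 in the group comparison.
- State that T0-adjusted differences at T32d and T39d reflect the whole regimen, before and after the laser. A between-group comparison of change from T25d can stay as a secondary analysis of the second course.

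The cost is that the sponsor gives up before/after p-values as evidence of efficacy. The before/after dimension of the objective remains, reported descriptively.
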